
(mITT) population will consist of all subjects who are enrolled in the study and receive at least 1 dose of study medication. who are not screen failures. The safety population which will consist of all subjects who receive at least one dose of KD025.
 
 • The safety population will consist of all subjects who receive at least one dose of KD025. The per protocol population will consist of subjects who have received at least 50% of study drug and have at least one evaluable response assessment. • The PK population which will consist of all subjects who receive at least one dose of study drug and have at least 1 post-dose PK sample drawn 
Demographics, subject disposition, and screening and baseline characteristics will be summarized for the mITT population and Per Protocol populations, where appropriate.
	
(mITT) population will consist of all subjects who are enrolled in the study and receive at least 1 dose of study medication.
 
 • The safety population will consist of all subjects who receive at least one dose of KD025. • The PK population which will consist of all subjects who receive at least one dose of study drug and have at least 1 post-dose PK sample drawn 
Demographics, subject disposition, and screening and baseline characteristics will be summarized for the mITT population.
	

Section 17.4 Activity Analysis
		

Original Text with Changes Shown (deleted text in strikethrough and added text in bold)	New wording	Brief Rationale/ Justification for Change

Secondary Endpoints
 
 • Number and percentage of KD025 in subjects with steroid-dependent cGVHD who have a best response of PR or CR • Change in cGVHD severity as based on the Physician-reported global cGVHD Activity Assessment • Change in symptom activity as based on cGVHD Activity Assessment Patient Self Report • Median FFS will be defined as the time from first dose of study drug to either the start of another treatment, relapse of the underlying disease, or death • Changes in corticosteroid and calcineurin inhibitor dose • To evaluate DOR. The DOR is defined as the time of initial response until documented progression. • To evaluate response by organ system. The response by organ system (PR and CR) will be assessed based on the 2014 NIH Consensus Development Project on Clinical Trials in cGVHD. • Overall Survival (OS) will be defined as the time from first dose of KD025 to the date of death due to any cause. Kaplan-Meier plots, descriptive statistics of OS and landmark OS at 6, 12, 18 and 24 months will be provided • Time to Next Treatment (TTNT) will be defined as the defined as the time from the first dose of KD025 to the start of additional systemic cGVHD therapy • Change in symptom burden/bother using the Lee cGVHD Symptom Scale 	
Secondary Endpoints
 
 • Number and percentage of KD025 in subjects with steroid-dependent cGVHD who have a best response of PR or CR • Change in cGVHD severity as based on the Physician-reported global cGVHD Activity Assessment • Change in symptom activity as based on cGVHD Activity Assessment Patient Self Report • Median FFS will be defined as the time from first dose of study drug to either the start of another treatment, relapse of the underlying disease, or death • Changes in corticosteroid and calcineurin inhibitor dose • To evaluate DOR. The DOR is defined as the time of initial response until documented progression. • To evaluate response by organ system. The response by organ system (PR and CR) will be assessed based on the 2014 NIH Consensus Development Project on Clinical Trials in cGVHD. • Overall Survival (OS) will be defined as the time from first dose of KD025 to the date of death due to any cause. Kaplan-Meier plots, descriptive statistics of OS and landmark OS at 6, 12, 18 and 24 months will be provided • Time to Next Treatment (TTNT) will be defined as the defined as the time from the first dose of KD025 to the start of additional systemic cGVHD therapy • Change in symptom burden/bother using the Lee cGVHD Symptom Scale 	
Statistical Analysis Plan is being updated to reflect these endpoints that will be analyzed.


Original Text with Changes Shown (deleted text in strikethrough and added text in bold)	New wording	Brief Rationale/ Justification for Change

Exploratory Endpoints
 
 • Changes in the expression of several cytokines (including IL-17A, IL-21, and IL-2) in plasma after KD025 administration to subjects with cGVHD • Changes in percentage of immune-cell subtypes (including Th17 and Treg cells) in whole blood after KD025 administration to subjects with cGVHD • Change in symptom burden/bother using the Lee cGVHD Symptom Scale 	
Exploratory Endpoints
 
 • Changes in the expression of several cytokines (including IL-17A, IL-21, and IL-2) in plasma after KD025 administration to subjects with cGVHD • Changes in percentage of immune-cell subtypes (including Th17 and Treg cells) in whole blood after KD025 administration to subjects with cGVHD 	

Appendix H: Drugs that Induce and Inhibit CYP3A4
		

Use of drugs that are moderate or strong inhibitors inducers of the CYP3A4 family of enzymes is prohibited in subjects who are receiving KD025. Other CYP3A4 inhibitors/ inducers should be used with caution.
 
Use of drugs that are moderate or strong inducers of the CYP3A4 family of enzymes (refer to source below) is prohibited in subjects who are receiving KD025.
	
Use of drugs that are strong inducers of the CYP3A4 family of enzymes is prohibited in subjects who are receiving KD025. Other CYP3A4 inhibitors/ inducers should be used with caution.
 
Use of drugs that are strong inducers of the CYP3A4 family of enzymes (refer to source below) is prohibited in subjects who are receiving KD025.
	
Based upon data from KD025-107 (KD025 Drug-Drug-Interaction study).

**SIGNATURE PAGE**

**DOCUMENT HISTORY**

Version	Author	Description
1.0		Nov 30, 2017 New Document
2.0		Revision The primary reasons for this new version include: 
 
• Change of study design: expansion cohort removed. In its place, there will be another new randomized, open-label Phase 2 study, KD025-213: “A Phase 2, Randomized, Multicenter Study to Evaluate the Efficacy and Safety of KD025 in Subjects with Chronic Graft Versus Host Disease After At Least 2 Prior Lines of Systemic Therapy”
 
• Add more definitions of duration of response in accordance with FDA type B meeting held on 01 May 2019
 
• Rearrange and add some secondary efficacy endpoints
 
• Correct the calculation of symptom score for the Lee cGVHD Symptom Scale
 

2.1		Revision The primary reasons for this new version include: 
 
• Add subsection of “Missing event dates”
 
• Change/clarify censoring rule for duration of response (DOR), time to new therapy (TTNT) and failure free survival (FFS)
 
• Clarify the definition of discontinuation of Corticosteroid
 

2.2		Revision The primary reasons for this new version include: 
 
• Add overall survival analysis as a secondary efficacy endpoint
 
• Add refractory to prior line status into subgroup analysis
 

2.3		Revision The primary reason for this new version is to move Lee symptom scale score from exploratory to secondary endpoint.

**LIST OF ABBREVIATIONS**

Abbreviation	Full Term
7-PtR	7-point reduction
ADI	Actual dose intensity
AE	Adverse event
ALP	Alkaline phosphatase
ALT	Alanine transaminase
ATC	American Therapeutic Chemical (Classification)
BID	Twice daily
BMI	Body mass index
C1D1	Cycle 1 Day 1
CI	Confidence interval
cGVHD	Chronic graft versus host disease
CM	Concomitant medication
CNI	Calcineurin inhibitor
CR	Complete response
CRF	Case report form
CSR	Clinical study report
CTCAE	Common Terminology Criteria for Adverse Events
DL co	Diffusing capacity of carbon monoxide
DO7-PtR	Duration of $\geq$ 7-PtR
DOR	Duration of response
ECG	Electrocardiogram
EOT	End of treatment
FEV1	Forced Expiratory Volume in One Second
FFS	Failure-free survival
HCT	Hematopoietic cell transplantation
FVC	Forced vital capacity
ICH	International Conference on Harmonisation
IL	Interleukin
LR	Lack of response
LSS	Lee cGVHD Symptom Scale
MedDRA	Medical Dictionary for Regulatory Activities
mITT	Modified Intent-to-treat
KPS	Karnofsky Performance Scale
NE	Not evaluable
ORR	Overall response rate
OS	Overall survival
PFT	Pulmonary function test

---

Abbreviation	Full Term
PD	Pharmacodynamics
PDI	Planned dose intensity
PK	Pharmacokinetics
PO	Oral(ly)
PPI	Proton pump inhibitor
PR	Partial response
PT	Preferred Term
RDI	Relative dose intensity
RV	Residual volume
QD	Once daily
ORR	Overall response rate
QTcF	Corrected QT interval using Fridericia's formula
SAE	Serious adverse event
SAP	Statistical Analysis Plan
SOC	System Organ Class
STB	Stable
TEAE	Treatment-emergent adverse event
TLC	Total lung capacity
TTNT	Time to next therapy
TTR	Time to response

---

## **1 INTRODUCTION**

Chronic graft versus host disease (cGVHD) remains a major complication of allogeneic hematopoietic cell transplantation (HCT) occurring in approximately 50% of transplant recipients and involving multiple organs. Subjects with cGVHD require prolonged immunosuppressive treatment for an average of 2 to 3 years from the initial diagnosis. Ten percent of those surviving for at least 7 years still require immunosuppressive treatment. Glucocorticoids, with or without calcineurin inhibitors (CNI), remain the standard initial treatment, but significant side effects and unsatisfactory outcomes, particularly for subjects with high-risk features of cGVHD, support the need for more effective and less toxic therapies.

This Statistical Analysis Plan (SAP) describes detailed statistical procedures to be used for study KD025-208 as specified in the protocol (Amendment No. 6, 15-Oct-2018): A Phase 2a, Dose-Escalation, Open-Label Study to Evaluate the Safety, Tolerability, and Activity of KD025 in Subjects with Chronic Graft Versus Host Disease. A primary clinical study report (CSR) analysis will be conducted 1 year after the last patient is enrolled. The pharmacokinetic (PK) and pharmacodynamic (PD) data will be analyzed and reported separately.

The SAP was written in accordance with the recommendations outlined in the International Conference on Harmonisation (ICH) E9 Guideline entitled “Guidance for Industry: Statistical Principles for Clinical Trials” and the most recent ICH-E3 Guideline, entitled “Guidance for Industry: Structure and Content of Clinical Study Reports.”

## **2 STUDY SUMMARY**

### **2.1 Study Objectives**

#### **2.1.1 Primary Objectives**

The primary objectives of this study are to evaluate:

- The activity of KD025 in subjects with steroid-dependent cGVHD and active disease in terms of partial response (PR) and complete response (CR), as defined

by the 2014 National Institute of Health (NIH) Consensus Development Project on clinical trials in cGVHD (see [Appendix A](#))

- The safety and tolerability of KD025 in subjects with cGVHD

### **2.1.2 Secondary Objectives**

The secondary objectives of this study are to evaluate:

- Duration of response (DOR)
- Time to response (TTR)
- Response by organ system
- Time to next therapy (TTNT)
- Changes in corticosteroid and CNI doses
- Failure-free survival (FFS)
- Overall survival (OS)
- Change in cGVHD severity as based on the Clinician-reported Global cGVHD Activity Assessment
- Changes in symptom activity using the cGVHD Activity Assessment Patient Self-Report ([Appendix C](#))
- Plasma PK of KD025 in subjects with cGVHD

### **2.1.3 Exploratory Objectives**

The exploratory objectives of this study are to evaluate:

- Changes in the expression of several cytokines (including interleukin [IL]-17A, IL-21, and IL-2) in plasma after KD025 administration
- Changes in percentage of immune-cell subtypes (including Th17 and Treg cells) in whole blood after KD025 administration
- Changes in symptom burden/bother using the Lee cGVHD Symptom Scale (LSS, [Appendix D](#))

## **2.2 Study Design**

This is a Phase 2a, open-label, dose-escalation, safety, tolerability, and activity study.

Subjects who have signed an Institutional Review Board/Independent Ethics Committee-approved informed consent form and who have met all of the inclusion/exclusion criteria will be enrolled. After approximately 4 weeks for screening, subjects will receive KD025 orally (PO) in 28-day cycles until disease progression or unacceptable toxicity occurs followed by 4 weeks of follow-up. In addition, subjects will be contacted every 8 weeks until study close-out to confirm survival status and the initiation of any anticancer treatment or any changes in treatment for cGVHD.

Sequential cohorts of approximately 16 subjects will be dosed at KD025 200 mg once daily (QD) PO, KD025 200 mg twice daily (BID) PO, and KD025 400 mg QD (Table 1). Prior to enrolling subsequent cohorts, the safety data in each previous cohort will be evaluated after 8 subjects have reached 2 months of treatment.

**Table 1. Cohorts in the Study**

Cohort	Number of Subjects	Treatment
Cohort 1	~16	200 mg KD025 QD
Cohort 2	~16	200 mg KD025 BID
Cohort 3	~16	400 mg KD025 QD

BID = twice daily; QD = once daily

### 2.3 Visit Schedule and Study Assessment

The flow chart of visit schedule and study assessments is given in the KD025-208 Protocol.

## 3 STATISTICAL METHODS

### 3.1 General Methods

#### 3.1.1 Computing Environment

All statistical programming and data analyses will be performed using SAS® Version 9.4 on Windows platform.

### **3.1.2 General Considerations**

General considerations for descriptive statistics and presentation for continuous and categorical data are given below.

Continuous data will be described using descriptive statistics: number of observations (n), mean, standard deviation, median, minimum, and maximum. Frequencies and percentages will be used for summarizing discrete (categorical) data. When categorical data are presented, the percent will be suppressed when the count is zero in order to draw attention to the nonzero counts. The denominator for all percentages, unless otherwise specified, will be the number of subjects in the cohort or in the specified analysis population.

Means, medians, standard deviations, and confidence intervals (CIs) will be reported to one decimal place more than the data reported on the case report form (CRF) or by the vendor. Minimum and maximum will be reported to the same number of decimal places displayed on the CRF or by the vendor. P-values will be reported to 4 decimal places.

Unless otherwise indicated, all summary tables will be presented by the following groups: Cohort 1 (KD025 200 mg QD PO), Cohort 2 (KD025 200 mg BID PO), Cohort 3 (KD025 400 mg QD PO), and Overall.

Because of the exploratory nature of the study, no adjustments will be made for the multiplicity of endpoints.

### **3.1.3 Study Day**

The Study Day for all assessments prior to the first study drug administration is calculated as the difference between the date of the event or measurement (e.g., adverse event [AE] onset date, assessment date, sample collection date) and the start date of study treatment. The day before the start of study treatment is Study Day -1.

The Study Day for all post-assessments after the first study drug administration is calculated as the difference between the date of the event or measurement (e.g., AE

onset date, assessment date, sample collection date) and the start date of study treatment plus one day. The first day of study treatment is Study Day 1.

### **3.1.4 Baseline**

Baseline value is defined as the valid and last non-missing value obtained within 28 days prior to subject receiving the first study medication, unless otherwise stated under the related assessment section. Baseline can be the day before the first study medication or on the same day as the first study medication if a pre-dose assessment is available. Subjects without data on a parameter before the first study medication will have a missing baseline for this parameter.

### **3.1.5 Handling of Incomplete or Missing Data**

Missing data will not be imputed in general and will be reported as missing in all listings. For categorical variables, patients with missing data are not included in calculations of percentages unless otherwise specified.

#### **Missing start and end dates for AE and concomitant medication (CM)**

The assumption will be the worst or most conservative judgment when imputing AE and CM start and end dates. The purpose of imputing a start date is to help define whether the AE/CM started while taking study drug.

For a partial or missing start date:

- If the day is missing, the first day of the month will be imputed. If the missing day is the same as the month of first dose of study drug, then the first dose date will be imputed.
- If the day and month are missing, the first day of January will be imputed. If the year is the same as the first dose date, then the first dose date will be imputed.
- If the day is completely missing, the first dose date will be imputed. If the end date suggests it could have started prior to this, the first day of January of the same year as the end date will be imputed.
- When imputing a start date, the start date will ensure that the new imputed date is sensible, i.e., is prior to the end date of the AE or CM.

For a partial or missing end date:

- If the day is missing, the last day of the month or the last assessment date, whichever is earlier, will be imputed.
- If the day and month are missing, the 31st of December or the last assessment date, whichever is earlier, will be imputed
- If the date is completely missing, there will be a need to look at whether the AE/CM is still ongoing before imputing a date. If the ongoing flag is missing, then it will be assumed that AE is still present, or CM is still being taken (i.e., do not impute a date). If the AE/CM has stopped, then the last assessment date will be imputed.

These data imputations are for categorization purpose only and will not be used in the listings.

If the assessment of the relationship of the AE to KD025 is missing, then it will be assumed that the AE is related to KD025 and the AE considered as such in the frequency tables of possibly related AEs. No imputation should be done at the data level.

### **Missing event dates**

Event date will be imputed only when day is missing, and the purpose of imputing an event date is to most conservatively calculate time to event.

If the day is missing, the first (mid, last) day of the month will be imputed for undesired (neutral, desired) event. If the missing day is the same as the month of first dose of study drug, then the first dose date will be imputed for undesired event.

These data imputations are for time to event calculation only and will not be used in the listings.

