### **3.8.2 Secondary Endpoints**

#### **3.8.2.1 Duration of Response (DOR)**

The primary definition of DOR is the time from first documentation of response to the time of first documentation of deterioration from best response (e.g., CR to PR, or PR to LR).

The secondary definition of DOR is the time from first documentation of response to the time of first documentation of lack of response.

The tertiary definition of DOR is the time from first documentation of response to the time of initiation of new systemic cGVHD therapy (which will be defined by clinical team review).

The quaternary definition of DOR is the time from first documentation of response to the time of first documentation of lack of response (as the secondary definition) but with durations summed for multiple response/lack of response episodes.

The DOR will be reported only for responders and statistics will include:

- Kaplan-Meier plots and descriptive statistics of DOR. The censoring rules in [Table 2](#) will be applied
- Landmark analyses: Number and percentage of subjects with response sustained for  $\geq 12$ ,  $\geq 20$ ,  $\geq 24$ ,  $\geq 32$ ,  $\geq 36$ , and  $\geq 48$  weeks

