**Table 2. Censoring Rules for Duration of Response**

DOR	Events	Censoring
Primary	
 
• Deterioration from best response
 
• Initiation of new systemic therapy for cGVHD
 
• Death
 
	
 
• Last documented response assessment
 
• If LR or initiation of new systemic therapy happens immediately after two or more missed response assessments, the event date should be set as four weeks (one cycle) after last documented response assessment prior this event
 

Secondary	
 
• Documented LR
 
• Initiation of new systemic therapy for cGVHD
 
• Death
 
	
Tertiary	
 
• Initiation of new systemic therapy for cGVHD
 
• Death
 
	Last response assessment or long term follow up assessment, whichever is the latest and available
Quaternary	
 
• Documented LR
 
• Initiation of new systemic therapy for cGVHD
 
• Death
 
 
With summation of DOR from multiple episodes
	Same with censoring rule for primary and secondary

cGVHD = chronic graft versus host disease; DOR = duration of response; LR = lack of response

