### 3.8.2.4 Time to Next Therapy (TTNT)

The TTNT will be measured as the time from first treatment to the time of new systemic cGVHD treatment (which will be defined by clinical team review), censored by last response assessment or long term follow up assessment, whichever is the latest and available. TTNT will be analyzed by the Kaplan-Meier survival method as well as the landmark analysis at 6, 12, 18, and 24 months.

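### The SAP's event-date imputation is bounded only by first dose, so duration of response can be negative and other times can fall short of documented event-free time

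*SAP*

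**What the plan says.** The rule is in SAP 3.1.5 under Missing event dates. It opens with its scope and aim (quoted up to the sentence's last word): "Event date will be imputed only when day is missing, and the purpose of imputing an event date is to most conservatively calculate time to". It continues: "If the day is missing, the first (mid, last) day of the month will be imputed for undesired (neutral, desired) event". One bound follows. If the event falls in the month of first dose, "then the first dose date will be imputed for undesired event". No other bound is stated.

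The endpoints that use these dates do not share a starting point:

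- DOR (SAP 3.8.2.1): "The primary definition of DOR is the time from first documentation of response to the time of first documentation of deterioration from best response". The tertiary definition is "the time from first documentation of response to the time of initiation of new systemic cGVHD therapy". SAP Table 2 counts new systemic therapy and death as events under all four definitions.
- Time to next therapy, TTNT (SAP 3.8.2.4): "The TTNT will be measured as the time from first treatment to the time of new systemic cGVHD treatment".
- Failure-free survival, FFS (SAP 3.8.2.7) and overall survival, OS (SAP 3.8.2.8): both run from first dose.

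Table 2 has one further dating rule for the primary, secondary and quaternary DOR. When lack of response or new therapy comes straight after two or more missed assessments, "the event date should be set as four weeks (one cycle) after last documented response assessment prior this event".

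**The concern.** The first-dose floor protects endpoints that start at first dose. It does not protect DOR, which starts later. If new therapy or death falls in the same calendar month as the first documented response and its day is unknown, the first of that month can precede the response. The duration is then negative, and the SAP does not tell the programmer what to do with it.

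A second effect reaches all four time-to-event endpoints. A subject may attend a visit mid-month, be documented as responding, untreated or alive, and have the event later that month. The rule places the event before that visit. A conservative date is the earliest one that fits the data; a date contradicted by a documented visit is not.

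At stake are the DOR landmarks at 12, 20, 24, 32, 36 and 48 weeks and the positions of Kaplan-Meier steps, in cohorts of 16 where one subject carries visible weight.

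**Working it through.** No figure in the plan depends on this rule, so there is none to reproduce. The check applies the rule to dates.

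**Inputs.** Imputation rule and first-dose bound: SAP 3.1.5. Origins and events: SAP 3.8.2.1 with Table 2, 3.8.2.4, 3.8.2.7, 3.8.2.8. Response assessments: Day 1 of each 28-day cycle from Cycle 2, plus end of treatment (Protocol 10.1). Planning response rate 25% with 16 per cohort (Protocol 17.2).

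**Assumptions of mine.** New therapy and death are undesired events (the SAP does not list which events are which). Durations are plain date differences. Dates are in 2017, with visits exactly 28 days apart.

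**Formulas.** Imputed date = 1st of the event month, or first dose if that is the same month. DOR = imputed date - first response. TTNT = imputed date - first dose.

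**Example A, negative DOR.** First dose 10 January; first response at Cycle 2 Day 1, 7 February; new therapy truly on 25 February, day not recorded. Imputed date: 1 February.
- DOR = 1 Feb - 7 Feb = -6 days (true value 18).
- TTNT = 1 Feb - 10 Jan = 22 days (true value 46), although the subject was known event-free at day 28.

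**Example B, a landmark flips.** Same first dose and first response; still responding at Cycle 5 Day 1, 2 May; new therapy truly on 12 May, day not recorded. Imputed date: 1 May.
- DOR = 1 May - 7 Feb = 83 days (true value 94).
- Response was documented to 2 May - 7 Feb = 84 days = 12 weeks, yet the subject fails the 12-week landmark.
- If durations are counted with one day added, moving every date except the imputed one a day later still flips it: response 8 February, Cycle 5 Day 1 on 3 May, imputed 1 May gives 82 + 1 = 83 days.

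**Example C, the first-dose bound itself.** First dose 2 January; event-free at the Day 22 visit (21 days after first dose); event truly on 30 January, day not recorded. The bound gives 2 January, so TTNT or FFS = 0 days (true value 28).

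**Enumeration.** All 365 first-dose days of one year; first response at Cycle 2, 3 or 4 Day 1; events uniform over a window after response; day always missing.

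| Event within | DOR negative |
|---|---|
| 28 days of response | 49% |
| 56 days | 25% |
| 168 days | 8% |

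The most negative DOR is -28 or -29 days. The imputed date precedes the last scheduled visit in 52% of cases. Mean shortening is 14.7 days and the maximum is 30 (an event on the 31st moved to the 1st). Negative times from first dose: none. These percentages are conditional on a missing day and do not predict how often it happens.

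**Does Table 2 catch Example A?** No. Two missed assessments after a documented response take at least 2 x 28 = 56 days, and a calendar month has at most 31. The re-dating rule also omits death and is not given for the tertiary DOR.

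**Weight of one subject.** 25% x 16 = 4 responders per cohort; 1/4 = 25 percentage points on a landmark percentage among responders.

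**The case against.** The best defence is that the rule is meant to shorten times and says so. For TTNT, FFS and OS it moves an event only within its correct month, in the intended direction. Negative DOR needs a coincidence: new therapy or death in the month of first response, with the day unknown. Deterioration and lack of response come from dated clinic assessments. New therapy is settled by clinical team review, concomitant medication is recorded to 28 days after the last dose, and the sponsor undertakes to seek dates of death (Protocol 13.1.2). A programmer would notice a negative duration.

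Most of this stands as a limit on frequency. It does not make the rule right. Noticing a negative value is not an instruction for handling it, and a value that is positive but contradicted by a visit, as in Example B, would not stand out. Missing days are plausible: changes in treatment after the study visits are learned through roughly 8-weekly contact by telephone, email, post or records (Protocol 8.8). Protocol 8.6 also puts the 28-day follow-up visit ahead of any new therapy. A therapy start later that month can therefore be imputed to before a visit that was treatment-free by design.

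Three stronger readings are tempting, and the documents do not support them.

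- *The rule has no lower bound.* The first-dose bound follows directly in the same paragraph.
- *All time-to-event endpoints can be negative.* Only DOR can; the others start at first treatment or first dose, where the bound sits.
- *The adverse-event start-date rule removes events from the treatment-emergent tables.* That rule reads: "If the end date suggests it could have started prior to this, the first day of January" of the end date's year is used instead of the first-dose date. The natural reading, under that section's worst-case aim, is an end date before first dose. Even on the looser reading, the shift to before treatment arises only when the end date falls in the first-dose year.

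**Conclusion.** The concern holds in limited form. The event-date rule is bounded by first dose but not by the endpoint's time origin or the last known event-free date. As written, it can give a negative DOR when new therapy or death with a missing day falls in the month of first response. It can also make DOR, TTNT, FFS and OS shorter than the event-free time on record.

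The size is at most 30 days per affected subject. A flipped DOR landmark is worth about 25 percentage points in a cohort with the planned 4 responders, and less with more responders. The total depends on how many event dates lack a day; if none do, the effect is nil. The overall response rate, the primary endpoint, does not use these dates. The point merits correction because a stated rule gives a wrong result and the repair is nearly free. It does not threaten the trial's main conclusion.

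**What to change.** Add one sentence to SAP 3.1.5, Missing event dates: *The imputed date will not be earlier than the latest of the first dose date, the time origin of the endpoint (first response for DOR) and the last date the subject was known to be event-free, nor later than the next documented contact or the data cut-off.*

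The floor applied to the examples:

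| Example | Rule as written | With the floor | True |
|---|---|---|---|
| A, DOR | -6 | 0 | 18 |
| A, TTNT | 22 | 28 | 46 |
| B, DOR | 83 | 84 | 94 |
| C, TTNT/FFS | 0 | 21 | 28 |

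No negative time remains and no imputed event precedes a documented event-free date. The times stay shorter than the truth, so the conservative aim is kept. The upper limit covers mid-month and end-of-month imputations. The neighbouring rule for adverse events and concomitant medication already requires its imputed start dates to be plausible, so the principle is not new to this SAP.

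The cost is one sentence and a few lines of code, with no new data. Optionally, the adverse-event rule could state that 1 January applies when the end date is before first dose; that is a wording clarification only.
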